9.3 Inclusion Criteria

Subjects who meet all the following criteria will be considered eligible to participate in the study:

1. Must provide signed and dated informed consent form (ICF) to participate in the study. Subjects must be able to (in the judgment of the Investigator) understand the nature of the study and all risks involved with participation in the study. Subjects must be willing to cooperate and comply with all protocol restrictions and procedures including study visits.
2. Male or female age ≥ 18 years at screening with documented diagnosis of SSc, as defined using the 2013 ACR/European League Against Rheumatism (EULAR) criteria (Appendix 1).
3. Has diffuse cutaneous form of SSc according to LeRoy and Medsger's criteria (Appendix 1).
4. Disease duration ≤ 5 years from the first non-Raynaud's phenomenon manifestation.
5. Has an mRSS of 15 to 45 units at screening and have clinical skin involvement proximal and distal to the elbows, knees, or both or any truncal involvement, with or without face involvement.
6. If disease duration is > 24 months defined as time from the first non-Raynaud phenomenon manifestation, subject must fulfil at least 1 of the criteria listed below that are indicative of active disease at screening:
 - a. A documentation of new skin involvement that occurred within the past 9 months, or
 - b. Increase in mRSS ≥ 3 units within the past 9 months, or
 - c. Presence of tendon friction rubs (TFRs) or,
 - d. C-reactive protein ≥ 6 mg/L, or
 - e. Erythrocyte sedimentation rate ≥ 28 mm/hr, or
 - f. Platelet count $\geq 330 \times 10^9/L$ (330,000/microliter).

NOTE: Investigator should exclude all other acute intercurrent illness if subjects fulfilling laboratory criteria (d, e, f) only.

7. Willing to follow restrictions regarding concomitant medications that are described in Appendix 2.

8. Female subjects who are non-lactating and have a negative urine pregnancy test at baseline visit prior to receiving the first dose of study drug.
9. Female subjects of childbearing potential and male subjects with partner of childbearing potential currently using/willing to use 2 effective methods of contraception including barrier method as described in Appendix 3.

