3.3 Sample Size and Power Considerations

The planned sample size of 72 is expected to provide power for the comparison between MT-7117 treatment group and placebo group for ACR CRISS score at Week 52. The calculation of sample size assumes a 2-sided alpha level of 0.05 and uses EAST (Version 6.5) for Wilcoxon Mann Whitney test. The randomized 72 subjects (36 subjects for MT-7117 and 36 subjects for placebo) with a 1:1 allocation ratio would provide 80% power to detect treatment difference of 0.35 (35% improvement on MT-7117 treatment group compared to placebo group) in ACR CRISS score at Week 52 with an associated standard deviation (SD) of 0.5.

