8.2.1 Primary Efficacy Endpoint

Primary Analysis

The primary treatment comparisons of interest are the ACR CRISS score for MT-7117 treatment group compared with placebo group at Week 52. MT-7117 treatment group includes all subjects treated with MT-7117 regardless down titrated or not. The treatment MT-7117 dose level at EOT will be compared with placebo as secondary analysis.

The primary endpoint will be summarized using descriptive statistics with interquartile range. The distribution of ACR CRISS score may not be normal distribution. For ACR CRISS score at Weeks 16, 26, 39, and 52 the comparison between MT-7117 treatment group and placebo group will be performed using the non-parametric analysis method. The point estimates and 2 sided 95% CIs and associated P-values for the difference between the treatment groups will be obtained using the Hodges-Lehman estimator corresponding to Wilcoxon's rank sum test. This non-parametric analysis will be performed with multiple imputation method, assuming missing at random. A supportive analysis will be performed at the same way for the primary endpoints using the per-protocol set (PPS). As a secondary analysis for the primary endpoint, the same analysis method will be applied to the intent to treat (ITT) population but the patients' data after taking rescue therapy will not be included. This approach will be performed to investigate a sensitivity for the primary analysis.

MI Step 1: The ACR CRISS score at week 52 will be multiply imputed using Fully Conditional Specification Method methodology under MAR assumption. The imputation for the missing ACR CRISS total score at week 52 will be conducted using all visit data of all subjects with available ACR CRISS total score up to week 52. The 50 different imputed datasets will be created using the MI procedure in SAS with 2023 for seed value. The following factors will be included in the imputation model: treatment group (TRT01P), randomization strata (the baseline autoantibody status of anti-RNA Polymerase III (positive or negative)).

[REDACTED]

[REDACTED]

[REDACTED]

[REDACTED]

[REDACTED]

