8.2.2 Secondary Efficacy Endpoints

Continuous endpoint

Change from baseline at 16, 26, 39 and 52 in the followings;

[figure not shown]
- HAQ-DI
- Patient Global Assessment
- %pFVC
- Physician Global Assessment
- mRSS

The above endpoint will be analyzed using mixed-effect model for repeated measures (MMRM). The model will include fixed categorical terms for treatment, randomization strata (autoantibody status of anti-RNA Polymerase III at screening (positive or negative)), visit, and treatment by visit interaction together with continuous covariate terms for baseline value of the endpoint and baseline value by visit interaction. An unstructured correlation structure will be used to model the within-subject variance covariance errors. Should convergence of the model fail (due to the small numbers of subjects in this study), other variance covariance matrices such as autoregressive [AR(1)] correlation matrix will be used if appropriate. The Kenward-Roger approximation will be used to estimate the denominator degrees of freedom. From the model

described above, adjusted (least squares [LS]) means and standard errors will be produced by treatment and visit. Difference in adjusted means at each visit (MT-7117 vs. placebo) with standard errors, 95% CIs and associated P values will also be produced. All available data from all subjects will be used in the analysis without any imputation.

ACR CRISS score responder (CRISS \geq 0.6)

Proportion of subjects with ACR CRISS score responder (CRISS \geq 0.6) at Weeks 16, 26, 39, and 52 will be analyzed using logistic regression model employing SAS GLIMMIX procedure. The model will include fixed categorical terms for the treatment group (TRTPN), the randomization factor (screening autoantibodyanti-RNA Polymerase III, positive or negative - STRTNC), visit, and treatment group (TRTPN) by visit interaction together with continuous covariate terms for baseline mRSS (BLMRSS). The treatment odds ratio at each visit will be estimated using a contrast (using ilink PDIFF options in LSMEANS). An unstructured correlation structure (UN) will be used to model the within-subject variance covariance errors. Should convergence of the model fail (due to the small numbers of subjects in this study), other variance covariance matrices such as autoregressive [AR(1)] or compound symmetry (CS) correlation matrix will be used if appropriate. The following SAS code will be used.

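### The CRISS rank comparisons, including the primary one, use no baseline covariate although the responder model on the same score adjusts for baseline mRSS: a missed gain in precision, not an error

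*SAP*

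**What the plan says.** For the primary endpoint, SAP 8.2.1 says that "the comparison between MT-7117 treatment group and placebo group will be performed using the non-parametric analysis method". The estimate, interval and P-value all come from the Hodges-Lehmann and Wilcoxon pair. Protocol 16.3.4.1 says the same. The method covers CRISS at Weeks 16, 26, 39 and 52, the per-protocol analysis, the analysis without post-rescue data, and each dose level against placebo. No covariate is named for the test. The readable imputation factors are treatment and the anti-RNA Polymerase III stratum. Redacted lines follow that list, and the MI Step 2 code is redacted too.

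SAP 8.2.2 treats related endpoints differently:

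- The responder model (CRISS of 0.6 or more) has terms for treatment, stratum, visit and treatment by visit, "together with continuous covariate terms for baseline mRSS (BLMRSS"). SAP section 10 records that the interaction of baseline mRSS with visit was dropped from this model; the main effect stayed.
- The MMRM for each of the five CRISS components includes "continuous covariate terms for baseline value of the endpoint".

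For the CRISS score itself, baseline mRSS appears in the readable text only as a subgroup factor, split at 25. Protocol 9.3 admits a wide range: "Has an mRSS of 15 to 45 units at screening".

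**The concern.** The responder endpoint is the primary score dichotomised. If baseline mRSS is worth adjusting for there, the same reasoning applies to the continuous score, and the SAP gives no reason for the difference. Its remark that CRISS may not be normally distributed justifies using ranks. It does not justify leaving out a covariate, because rank analysis of covariance is also rank-based.

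The scoring equation offers a route by which baseline could matter. CRISS uses absolute changes, at 0.81 logits per mRSS unit, so the same proportional skin improvement scores very differently at the two ends of the entry range.

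At stake is precision in a small trial. With 36 per arm, one standard error of chance imbalance in mean baseline mRSS is √(2/36) = 0.24 SD, and an unadjusted test makes no allowance for it.

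**Working it through.** **Inputs (SAP 3.3).** On the test and alpha: "The calculation of sample size assumes a 2-sided alpha level of 0.05 and uses EAST (Version 6.5) for Wilcoxon Mann Whitney test". The other inputs are 36 per arm, a target power of 80%, a between-arm CRISS difference of 0.35, and an SD of 0.5.

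**Step 1: reproduce the plan's power.** Noether's formula under a normal shift:

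- P(X > Y) = Φ(0.35 / (0.5·√2)) = 0.690
- N for 80% power = (1.960 + 0.842)² / (12 · 0.25 · 0.190²) = 72.7 (0.190 is 0.6897 − 0.5, unrounded in the calculation)
- Power at N = 72 = Φ(√(3·72) · 0.1897 − 1.960) = Φ(2.788 − 1.960) = 79.6%

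The stated 80% holds for the unadjusted test.

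**Step 2: the effect of adjusting.** Let r be the rank correlation between baseline mRSS and Week 52 CRISS. Adjustment multiplies the residual variance by 1 − r², so power = Φ(2.788/√(1 − r²) − 1.960), and the equivalent unadjusted sample size is 72/(1 − r²). The documents give no r, so it is varied. The last two columns simulate a normal shift (20,000 trials per row, 36 per arm), using Quade's form of rank analysis of covariance.

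| r (assumed) | Power by formula | Gain (points) | Equivalent N | Simulated Wilcoxon | Simulated rank ANCOVA |
|---|---|---|---|---|---|
| 0 | 79.6% | 0 | 72 | 81.4% | 81.1% |
| 0.1 | 80.0% | 0.4 | 72.7 | 81.5% | 81.5% |
| 0.2 | 81.2% | 1.6 | 75 | 81.3% | 82.4% |
| 0.3 | 83.2% | 3.6 | 79 | 81.7% | 84.2% |
| 0.4 | 86.0% | 6.4 | 86 | 81.1% | 86.9% |
| 0.5 | 89.6% | 10.0 | 96 | 81.0% | 89.8% |

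Type I error of the adjusted test stayed between 4.9% and 5.3%.

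**Step 3: the bounded score.** CRISS lies between 0 and 1, so a normal shift is only a guide. Drawing component changes and passing them through the protocol Appendix 4 equation (3,000 trials per setting, component variances assumed) gave 60.7% for Wilcoxon against 63.3% for rank ANCOVA at r = 0.28, and 65.4% against 64.7% at r = 0. These runs are not calibrated to 80% power; only the differences are informative.

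**Step 4: is a material r plausible?** With the other four components unchanged, CRISS = 1/(1 + exp(5.54 − 0.81·fall)).

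- A 25% fall in mRSS gives 0.08 from a baseline of 15 (fall 3.75), 0.38 from 25, 0.63 from 30 and 0.97 from 45.
- Reaching 0.6 on skin alone needs a fall of (5.54 + ln 1.5)/0.81 = 7.3 units, which is 49% of 15 but 16% of 45.

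This supports some correlation if change scales with baseline. Even so, a rough simulation with mRSS change proportional to baseline gave r of only 0.11 to 0.16, and about 0 when change was independent of baseline.

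**The case against.** The strongest reply is that nothing here is wrong. The unadjusted Wilcoxon test is valid under randomisation, it is the protocol's primary analysis, the trial was sized on it, and its power reproduces. All of that stands.

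The gain also rests on a correlation the documents do not supply. A reader might infer that the SAP declares baseline mRSS prognostic. It only includes it in a model, and gives no size for its effect.

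A reader might also infer that a low baseline caps the score. It does not: falls of 8, 10 and 15 units on skin alone give 0.72, 0.93 and above 0.99, so a subject entering at 15 can approach 1.0. The argument from proportional change survives; an argument from a ceiling does not.

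Nor is the primary test the only efficacy analysis in the readable text without a baseline term. CRISS at Weeks 16, 26 and 39, and the per-protocol, rescue-excluded and dose-level CRISS comparisons, share its method. The SAP is consistent for the continuous score; the contrast is with other endpoint types.

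Finally, the redactions mean that the imputation model may already contain baseline mRSS. Its absence from the visible list is not evidence that it is missing.

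What remains is that no readable reason is given for leaving out of the rank test a covariate that the responder model on the same score keeps.

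**Conclusion.** The point holds as a missed precision gain. It is not an error, and a reader should not conclude that the trial is underpowered for its stated assumptions.

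The gain is under 2 points of power for r up to 0.2 and becomes material from about 0.3 (3.6 points, worth about 7 subjects); at 0.4 it is 6.4 points, worth about 14. If baseline mRSS is unrelated to CRISS, the loss is below 1 point: 0.3 in the normal simulation and 0.7 in the CRISS simulation. The cost is therefore negligible and the benefit uncertain but possibly useful with 36 per arm.

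This rests on three assumptions: the values of r, a normal shift for the main table, and a redacted MI Step 2 code that does what the visible text describes. The randomisation stratum is also not named for the rank test; that is a separate matter and is not counted here.

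**What to change.** Before unblinding, amend SAP 8.2.1 as follows.

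- **MI Step 2.** In each imputed dataset, rank CRISS and baseline mRSS across both arms and regress the CRISS ranks on treatment and the baseline ranks. Apply this to the Week 52 comparison and to the other CRISS analyses that share the method.
- **MI Step 3.** Pool the rank-scale treatment coefficient and its standard error with MIANALYZE. Take the P-value, estimate and 95% interval from that one model. Pairing an adjusted P-value with the unadjusted Hodges-Lehmann interval would leave the reported estimate no more precise and could let test and interval disagree.
- **Supportive analysis.** Keep the unadjusted Wilcoxon P-value and Hodges-Lehmann shift with its interval, labelled as supportive, so that a result on the CRISS scale is still reported.
- **MI Step 1.** Include baseline mRSS among the predictors if the redacted lines do not already do so.
- **SAP section 10.** Record the change from the protocol.

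If the unadjusted test is kept as primary, state why, and name the adjusted analysis as a sensitivity analysis.

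The cost is SAP wording and programming, with no new data. SAP section 1 lets the SAP supersede the protocol on statistical detail and has it finalised before database lock. The drawbacks are the small power loss if r is zero and a primary estimate on the rank scale. That estimate can still be read: without adjustment, the difference in mean ranks equals N·(P(X > Y) − 0.5), which at the design assumptions is 72 × 0.190 = 13.7 ranks.

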7.1.2 Efficacy assessments

7.1.2.1 Primary Efficacy Endpoint

The primary efficacy endpoint is the ACR CRISS score which is a composite endpoint assessed in a 2-step process that calculates the probability of improvement for each subject ranging from 0.0 (no improvement) to 1.0 (marked improvement).

Step 1: Subjects who develop new or worsening of cardiopulmonary and/or renal involvement due to systemic sclerosis are considered as not improved (irrespective of improvement in other core items) and assigned a probability of improving equal to 0.0. Specifically, if a subject develops any of the following

- New scleroderma renal crisis (See protocol for definition)
- Decline in %pFVC $\geq 15\%$ (relative), confirmed by another %pFVC within a month, high resolution computer tomography (HRCT) to confirm ILD (if

previous high-resolution computer tomography of chest did not show ILD) and %pFVC below 80% predicted*

- New onset of left ventricular failure (defined as left ventricular ejection fraction $\leq 45\%$) requiring treatment*
- New onset of pulmonary arterial hypertension (PAH) on right heart catheterization requiring treatment.* PAH is defined as mean pulmonary artery pressure ≥ 20 mm Hg at rest and an end-expiratory pulmonary artery wedge pressure ≤ 15 mm Hg and a pulmonary vascular resistance > 3 Wood units

*= Attributable to systemic sclerosis.

The step 1 is up to medical judgement and the data in the CRF will be used directly for deriving the endpoint. If the data in the CRF is “NOT done” or “missing” then the ACR CRISS score will be missing.

Step 2: For the remaining subjects, Step 2 involves computing the predicted probability of improving for each subject using the following equation (equation to derive predicted probabilities from a logistic regression model):

$$\frac{\exp[-5.54 - 0.81 * \Delta_{MRSS} + 0.21 * \Delta_{FVC\%} - 0.40 * \Delta_{Pt-glob} - 0.44 * \Delta_{MD-glob} - 3.41 * \Delta_{HAQ-DI}]}{1 + \exp[-5.54 - 0.81 * \Delta_{MRSS} + 0.21 * \Delta_{FVC\%} - 0.40 * \Delta_{Pt-glob} - 0.44 * \Delta_{MD-glob} - 3.41 * \Delta_{HAQ-DI}]}$$

where Δ_{MRSS} indicates the change in MRSS from baseline to each visit, $\Delta_{FVC\%}$ denotes the change in FVC% predicted from baseline to each visit, $\Delta_{Pt-glob}$ indicates the change in subject global assessment, $\Delta_{MD-glob}$ denotes the change in physician global assessment, and Δ_{HAQ-DI} is the change in HAQ-DI. All changes are absolute change (Time₂–Time_{baseline}).

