The Physician Global Assessment is used to assess the physician's rating of overall health of the subject. Physicians rate the perceived health of the subject on an 11 point

scale from 0 (excellent) to 10 (extremely poor). Higher scores indicate worse disease in terms of severity, damage, or overall disease, but there is no standardization for the scale (Pope 2011). A negative change from baseline indicates improvement. Expert consensus has suggested a range of 8-13 units on Global VAS scale 100 mm. for the MCID (Gazi et al. 2007). Therefore, -0.8 to -1.3 points will be defined as MCID in this assessment.

- Modified Rodnan Skin Score (MRSS)

The mRSS will be assessed by a qualified and trained Efficacy Assessor to limit the variability. The same Efficacy Assessor will measure skin thickness on 17 different body areas on a scale from 0 (normal) to 3 (severe). Global average scoring method (The assessor scores individual sub-areas, as needed for differences within large areas and takes average of sub-areas to attain the score for that overall area) will be used as a scoring technique in this study. Worsening of skin fibrosis as measured by the mRSS score was associated with a disease progression and overall mortality in subjects with dcSSc, indicating that the mRSS is a good surrogate marker for disease progression. The mRSS is a measure of skin thickness across 17 different body sites and has a range of 0 to 51 in whole units. Total score is derived from the sum of the 17 different body areas. If at least one domain score is missing, the total score will be regarded as missing. The MCID has been reported by Dinesh Khanna 2019 to be 3 to 5 units for dcSSc patients.

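### MI Step 1 imputes the Week 52 CRISS total and, on the visible text, makes no use of Week 52 components that were observed; component-level imputation would be more precise, with a small gain for the trial

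*SAP*

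**What the plan says.** SAP 8.2.1 (Primary Efficacy Endpoint, MI Step 1) says that the Week 52 score "will be multiply imputed using Fully Conditional Specification Method methodology under MAR assumption". The data used are described in one sentence: "The imputation for the missing ACR CRISS total score at week 52 will be conducted using all visit data of all subjects"; the subjects meant are those for whom a CRISS total exists. On predictors it says "The following factors will be included in the imputation model: treatment group (TRT01P), randomization strata", the stratum being anti-RNA polymerase III status. The lines after that are redacted. "The 50 different imputed datasets will be created using the MI procedure in SAS".

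SAP 7.1.2.1 obtains the score by "computing the predicted probability of improving for each subject using the following equation", which uses the changes in mRSS, %pFVC, patient global, physician global and HAQ-DI. No rule covers a visit at which only some of the five are available. The same section sets the score to missing when the Step 1 entry (new organ involvement) is missing or not done in the CRF. For mRSS, SAP 7.1.2.2 says "If at least one domain score is missing, the total score will be regarded as missing".

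Protocol 16.3.4.1 asks only for multiple imputation under missing at random. SAP section 1 states that the SAP takes precedence over the protocol on analysis details.

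**The concern.** A partly observed Week 52 assessment has no CRISS score, and the visible imputation model then predicts that score from earlier totals, treatment and stratum. Measurements taken on the day of the primary endpoint, which enter the score directly, are not named as informing the imputed value.

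The documents show several ways this can happen:
- one unscored skin site out of 17 makes mRSS missing (SAP 7.1.2.2);
- the physician global form offers a Not Known box (Protocol Appendix 8);
- HAQ-DI cannot be scored with fewer than six of eight categories (SAP 7.1.2.2);
- FVC may have no usable value at the visit;
- a missing Step 1 entry voids the score even when all five components are observed (SAP 7.1.2.1).

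At stake is avoidable noise in the primary comparison of a 72-subject trial planned at 80% power with no stated dropout allowance. The matter is precision. Nothing here shows bias.

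**Working it through.** **1. The plan's own power figure.** Inputs from SAP 3.3: 36 per arm, difference 0.35, SD 0.5, two-sided alpha 0.05, Wilcoxon Mann-Whitney test.
- Standardised difference: 0.35/0.5 = 0.70.
- For a normal shift, P(X>Y) = Φ(0.70/√2) = 0.690.
- Noether power: Φ(√(3N)·(P − 0.5) − 1.96) = Φ(14.70 × 0.1897 − 1.96) = Φ(0.83) = 79.6%. The N for 80% is 72.7.
- Simulation of the test (40,000 runs) gives 81.5%.

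The stated 80% is reproduced.

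**2. How much each component carries.** The coefficients come from SAP 7.1.2.1. The SDs of change are assumptions, because the documents give none.

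| Component | Coefficient (absolute) | Assumed SD | Product, logit scale |
|---|---|---|---|
| mRSS | 0.81 | 5-7 | 4.05-5.67 |
| %pFVC | 0.21 | 8-9 | 1.68-1.89 |
| HAQ-DI | 3.41 | 0.5-0.6 | 1.71-2.05 |
| Patient global | 0.40 | 2.2-2.5 | 0.88-1.00 |
| Physician global | 0.44 | 2.0-2.2 | 0.88-0.97 |

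If a global, FVC or HAQ-DI is missing, the four observed components include mRSS and pin the score down well. If mRSS is missing, they recover much less.

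**3. Error of the imputed score.** Five correlated components were simulated at Weeks 16, 26, 39 and 52 (200,000 subjects per scenario; SDs as above; between-component correlation 0.1-0.5; adjacent-visit correlation 0.6-0.9) and the SAP equation applied. Two predictions of the Week 52 score were compared: (a) from treatment and the three earlier totals; (b) from the observed Week 52 components, with the missing one predicted from treatment and the other component data and the score recomputed. A further simulation, also on assumed SDs and correlations, scored a single random imputed draw.

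| Missing | Prediction RMSE, total | Prediction RMSE, component | Single-draw RMSE, total | Single-draw RMSE, component |
|---|---|---|---|---|
| A global | 0.24-0.39 | 0.03-0.08 | 0.37-0.52 | 0.05-0.11 |
| FVC or HAQ-DI | 0.24-0.39 | 0.05-0.15 | 0.37-0.52 | 0.10-0.20 |
| mRSS | 0.24-0.39 | 0.11-0.31 | 0.37-0.52 | 0.27-0.41 |

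The two scales agree. A draw adds imputation noise of about the same size as the prediction error, so its RMSE is about √2 times larger: 0.24 × 1.414 = 0.34 and 0.39 × 1.414 = 0.55, which bracket 0.37-0.52. On the prediction scale, the total-score error is larger by about 4.5-11 times (a global), 2.4-5.6 times (FVC, HAQ-DI) and 1.2-2.3 times (mRSS).

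**4. Trial level.** Take effective N = 72 − m(1 − R²), where m is the number of partly missing subjects and R² is the share of score variance that the imputation recovers. Illustrative R² is 0.27-0.65 for the total and 0.60-0.98 for components.
- m = 2, total: N = 72 − 2 × 0.73 = 70.5 to 72 − 2 × 0.35 = 71.3; power 78.8-79.2%. Components: N = 71.2 to 72.0; power 79.2-79.6%. Difference at matching ends: about 0.4 point.
- m = 7, total: N = 72 − 7 × 0.73 = 66.9 to 72 − 7 × 0.35 = 69.6; power 76.6-78.2%. Components: N = 69.2 to 71.9; power 78.0-79.5%. Difference at matching ends: 1.3-1.4 points; widest contrast 79.5 − 76.6 = 2.9.

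If the whole visit is missed, no Week 52 components exist and there is nothing to recover.

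**The case against.** The strongest reply is that partial missingness should be uncommon and its cost slight.
- SAP 7.1.2.2 and 7.2 allow QA-failed FVC values to be used where none passed, subject to a legible flow loop and approval at blinded review. Protocol 11.5 has a rejected FVC from Week 16 onwards repeated within 2 weeks.
- HAQ-DI tolerates two missing categories.
- The Week 52 window spans Days 320-379, and unscheduled values can fill it.
- In a simulation with 7 of 72 subjects partly missing, the pooled Mann-Whitney probability was 0.651 under total-score imputation, against 0.654-0.655 with complete data; its SD rose by about 3-5%.
- The redacted lines may add predictors, and the reference to all visit data could be read more broadly than totals.

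Most of this stands, and it limits the size of the point. It does not supply a rule for a partly observed visit, and no visible text uses the components.

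A reader might infer more than the documents support:
- *A QA-rejected FVC makes the score missing.* Rejection alone does not.
- *Imputed values fall outside 0-1 and do not resemble CRISS scores.* Unbounded linear draws did so in 26-31% of simulated cases, but the actual model is redacted. Fully conditional specification also allows predictive mean matching, which returns only observed values.
- *Imputation is much poorer whichever component is missing.* That fits four of the five; for mRSS the difference is moderate.
- *The observed measurements are lost to the trial.* They remain in the secondary mixed models (SAP 8.2.2), and earlier totals still inform the imputed score.

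**Conclusion.** The point holds as one of efficiency and completeness. On the visible text, a partly observed Week 52 assessment contributes none of its observed components to the primary imputation, and neither that case nor a missing Step 1 entry with all components observed has its own rule. Component-level imputation was more accurate in every scenario examined, clearly so when a global, FVC or HAQ-DI is missing and moderately so for mRSS. The expected benefit is about 0.5 power point with 2 such subjects and 1-3 points with 7 of 72.

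These sizes rest on assumed SDs, correlations and R² values, and on a number of partly missing subjects that the documents do not give. That the components are absent from the model is read from unredacted text and is not proven. The single-draw errors should not be quoted as prediction errors, because they include noise that multiple imputation averages over 50 datasets. Low to moderate priority.

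**What to change.** In MI Step 1, where the Week 52 assessment is partly observed, impute only the missing component change or changes by fully conditional specification, from treatment, stratum and that component's earlier changes. Keep the observed Week 52 components and recompute CRISS in each of the 50 datasets. Total-score imputation can remain where the whole visit is missing.

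State separately how a missing or not-done Step 1 entry is handled when the five components are observed; recomputing the equation does not settle that case.

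Adding the observed same-visit components linearly to the model for the total is a weaker alternative: its single-draw error was still 0.29-0.42.

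The cost is SAP wording and modest programming before database lock. The downside is a somewhat larger imputation model for 72 subjects, so predictors per component should be kept few.
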